8.2.5. QUALITY-OF-LIFE QUESTIONNAIRE IN 30 QUESTIONS (QLQ-C30)

The health related quality-of-life in cancer patient will be measured with the Quality-of-Life Questionnaire-C30 (QLQ-C30; Copyright © 2002 EORTC Quality-of-Life Group). This core questionnaire contains 30 items divided into functional scales, symptom scales, single items and global quality-of-life. It will be completed at enrolment and at Visit 2 as specified in Sections 16.1 and 16.2 Study Schedule.

8.3. INFORMATION ON GENERAL HEALTH STATUS

This is an observational study and it does not therefore interfere with the way the Investigator is managing patients.

The Investigator remains responsible for adequate patient management and for a clinical assessment of the study participants before discharge from the study as well as for the set up of a discharge plan, if needed.

In addition to records of observations made at specific times, symptoms related to analgesic treatment will be recorded in the clinical study records throughout the study.

The following parameters will be collected during this study at specific timepoints as described in the Study Schedule (Sections 16.1 and 16.2):

- Symptoms related to pain treatment (e.g. nausea).
- Potential historical laboratory analysis data (biochemistry and hematology data) defined as the most recent safety laboratory analysis obtained within one month before the screening and/or ongoing laboratory safety analysis and urine analysis, if available, performed as part of patient management by the Investigator. In case several safety laboratory analysis are performed during the study, only one per week will be recorded.
- Abbreviate physical examination at screening and Visit 2..

Further routine medical assessments may be performed during the study, if warranted or when clinically indicated.

8.3.1. SYMPTOMS MONITORING

Definition of Adverse Event (AE)

Typically, a clinical study AE is any untoward medical occurrence in a patient or clinical study patient administered an investigational medicinal product and which does not necessarily have a causal relationship with this treatment.

This does not apply to this observational study. Nevertheless the symptoms related to analgesic treatment(s) will be collected.

Symptoms Collection and Reporting

At enrolment, study site personnel will record the occurrence, time of onset, nature and severity of symptoms related to analgesic treatment. Up to Visit 2, site personnel will record any change in the occurrence and nature of symptoms related to analgesic treatment or having an impact on pain evaluation. The nature, time of onset, duration, severity will be documented and each symptom will be classified by the most suitable term from a version of a Medical Dictionary for Regulatory Activities (MedDRA) agreed by the Sponsor and other parties involved in the study.

The condition of each patient will be monitored throughout the study. In addition, any sign or symptom related to pain treatment will be observed and elicited at least at each visit by open questioning, such as “How have you been feeling since you were last asked?”

Patients will also be encouraged to report spontaneously any symptom occurring at any other time during the study.

8.3.1.1. Symptom Intensity

The clinical intensity of symptom will be classified as:

- Mild: the event results in a mild or transient discomfort, not requiring intervention or treatment; does not limit or interfere with daily activities (e.g. mild headache, insomnia),
- Moderate: the event is sufficiently discomforting so as to limit or interfere with daily activities; may require interventional treatment (e.g. fever requiring antipyretic medication),
- Severe: the event results in significant symptoms that prevent normal daily activities; may require prolonged interventional treatment, hospitalization or invasive intervention (e.g. anemia resulting in blood transfusion).

8.3.2. SERIOUS ADVERSE EVENT AND REPORTING

Not applicable (observational study). Nevertheless, if a patient is withdrawn from the study because of an SAE, this information will be collected.

8.4. STUDY PROCEDURE PRIORITY ORDER

Figures 2 to 5 in Section 4.1 are describing the sequence of procedures at each visit.

8.5. COMPLIANCE TO STUDY PROCEDURES

Compliance is the adherence to trial-related requirements, to GCP, to protocol and to regulatory rules and regulations.

8.5.1. COMPLIANCE TO PROTOCOL

Every attempt will be made to select patients who have the ability to understand and comply with instructions. Non-compliant patients may be discontinued from the study.

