5. POPULATION RECRUITMENT, ENROLMENT AND WITHDRAWAL

5.1. DEFINITIONS

Screening Failure:

A patient is considered as a screening failure when he/she is screened but not enrolled in the study as not meeting eligibility criteria.

Patient Enrolment:

A patient is considered as enrolled in the study when he/she meets all eligibility criteria and he/she performs CPAs at Visit 1 or Visit 1A.

Patient Dropout:

A patient will be considered as dropout when, for any reason, he/she withdraws from the study or is discontinued from the study prior to study completion.

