5.8. PATIENT WITHDRAWAL, DISCONTINUATION AND REPLACEMENT

5.8.1. WITHDRAWAL /DISCONTINUATION CRITERIA

All patients are free to withdraw their consent to participate in the study at any time, for any reason, specified or non-specified, and without penalty.

The Sponsor and/or the Investigator for some possible reasons listed below may discontinue a patient from the study:

- If, in the opinion of the Investigator and/or the Sponsor, patient's general health status contra-indicates patient continuation in the study,
- The Investigator or delegate decides that the study participant should be withdrawn from the study,
- Non-compliance of the patient with study instructions, such as the patient fails to return to the study site for a scheduled visit and/or does not respond to the attempts of the study site staff to contact him/her (considered as lost to follow-up).

All cases of discontinuation will be discussed between the Investigator and the Sponsor.

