6. STUDY TREATMENT

6.1. STUDY DRUG AND TREATMENT OF PATIENTS

No IMP will be administered in this observational study.

Patients will be treated by the Investigator for pain relief exactly as they would normally be based on their needs and clinician practice.

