8.5.3. COMPLIANCE TO ANALGESIC PATIENT 'S THERAPY

Patient's compliance to prescribed analgesic medication will be assessed at each visit by direct questioning and checking diary. The investigator will evaluate if patient fails to take more than 50% of the prescribed analgesic medication for the visit interval.

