10. STATISTICAL ANALYSES

10.1. DATA ANALYSIS PLANS

10.1.1. GENERAL CONSIDERATIONS

For all enrolled patients, pharmacodynamic analyses will be conducted on the full analysis set.

All tests of treatment effects will be conducted at a two-sided alpha level of 0.05, unless otherwise stated.

Additional exploratory analyses of the data will be conducted as deemed appropriate.

Detailed plan for the statistical methods for the safety and other variables will be provided in a Statistical Analysis Plan (SAP). This plan will be finalized prior to database lock.

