2.5 Secondary Endpoints

- Individual analgesic treatment efficacy: Patient's daily APS and the linear regression coefficient of its daily evolution
- Individual analgesic treatment efficacy: Patient's change from baseline of
 - Pain severity, as measured by the weekly means of the daily Worst Pain Score (WPS),
 - Pain severity and interference as measured by the Brief Pain Inventory (BPI),
 - Investigator and Patient Global Assessment of Changes (IGAC and PGAC),
 - Pain intensity measured after Clinical Pain Assessments (CPAs) at Visit 2,
 - Quality-of-Life Questionnaire in 30 questions (QLQ-C30).
- Correlation between pain severity and clinical pain assessment as measured by:
 - Pain severity, as measured by the weekly Average Pain Score (APS) at Visit 1 and 2,
 - Pain intensity measured after Clinical Pain Assessments (CPAs) at Visit 1 and 2.

Variables used as predictive factors rather than as endpoints are described hereunder in Section 4.2.

3 Summary of Study Design

See the latest protocol version.

4 Populations for Analyses

Statistical analysis and data tabulation will be performed using the population of completers unless specified otherwise. This set includes all data from patients who have been screened, included and who completed the study (no drop-outs).

For the interim analysis, only patients who completed the study before the interim database transfer will be included.

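### Discontinuing patients for non-compliance in an observational study, then analysing completers only, creates avoidable selection of unknown direction on behaviour that may be related to the traits under study

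*Protocol*

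**What the plan says.** Protocol 8.5 defines compliance broadly: "Compliance is the adherence to trial-related requirements, to GCP, to protocol and to regulatory rules and regulations". Its subsections then cover protocol, timing, analgesic intake, visits and diary. Protocol 8.5.1 adds, without a threshold, "Non-compliant patients may be discontinued from the study". Protocol 5.8.1 gives as a ground for discontinuation "Non-compliance of the patient with study instructions, such as the patient fails to return to the study site for a scheduled visit", and goes on to patients who do not respond to contact. On analgesic intake, Protocol 8.5.3 says only "The investigator will evaluate if patient fails to take more than 50% of the prescribed analgesic medication for the visit interval"; no consequence follows.

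Under Protocol 5.1 a dropout is anyone for whom "he/she withdraws from the study or is discontinued from the study prior to study completion". Protocol 5.8.3 foresees no replacement. On the analysis set, Protocol 10.1.1 says "For all enrolled patients, pharmacodynamic analyses will be conducted on the full analysis set". SAP section 4 says of its population "This set includes all data from patients who have been screened, included and who completed the study (no drop-outs"; the SAP introduction gives the name full analysis set to the same completers. The SAP's list of changes from protocol (1.2) does not mention this narrowing.

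On care, Protocol 6.1 says "Patients will be treated by the Investigator for pain relief exactly as they would normally be based on their needs and clinician practice".

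**The concern.** In a drug trial, a non-compliance rule can protect the patient or the meaning of the exposure. Here neither reason applies: no product is given and usual care continues whether or not the patient stays in the study. Ending participation only loses data. What is lost includes the Visit 2 BPI, PGAC, IGAC, QLQ-C30 and clinical pain assessments, none of which needs a complete diary.

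The primary objective asks whether disease, history, personality traits and expectation predict how well pain management works. Compliance could plausibly vary with locus of control, anxiety, catastrophizing or expectation. Removing patients because of their compliance, and then analysing only those who remain, selects on a variable that may be linked to both predictor and outcome. The protocol itself creates these dropouts, so a wider analysis set alone would not recover Visit 2 data that were never collected.

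**Working it through.** **The plan's own figures.** There is no power calculation to reproduce: Protocol 4.2.1 states that no hypothesis test or precision target was used. The only figures are up to 180 enrolled and about 140 completers, an implied loss from all causes of 1 − 140/180 = 22.2%. No share is attributed to non-compliance.

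**Direction of bias.** Simulation with 2,000,000 patients: trait T; compliance A = aT + error; relief Y = bA + dT + error. The least compliant are removed and the slope of Y on T is compared between completers and the full cohort. All parameters are assumptions. The 22.2% column is an upper bound, since it assigns every planned loss to non-compliance. Entries are completer slope divided by full-cohort slope.

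| Scenario | 5% removed | 10% | 22.2% |
|---|---|---|---|
| Trait acts only through compliance (a=0.3, b=0.5, d=0) | 0.83 | 0.73 | 0.59 |
| Same, but only half of those below the cut-off removed | 0.88 | 0.86 | 0.91 |
| Plus direct effect of the same sign (d=0.2) | 0.92 | 0.88 | 0.82 |
| Plus direct effect of opposite sign (d=−0.3) | 1.18 | 1.27 | 1.42 |
| Plus direct effect of opposite sign (d=−0.2) | 1.53 | 1.82 | 2.26 |
| Compliance has no effect on relief (b=0, d=0.2) | 1.00 | 1.00 | 1.00 |
| Trait unrelated to compliance (a=0, d=0.2) | 1.00 | 1.00 | 1.00 |
| Unmeasured factor raises compliance and lowers relief (a=0.3, b=0.3, d=0.1) | 1.03 | 1.05 | 1.08 |

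The result can therefore be attenuation, no change or inflation.

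**Size under attenuation.** Assume a = 0.4, b = 0.5 and effect wholly through compliance, so the true r = 0.4 × 0.5 = 0.20. With v the variance of A among those kept,

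r_obs = abv / √[(1 − a²(1 − v))(1 − b²(1 − v))].

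Power at two-sided 0.05 is Φ(√(n−3)·atanh(r) − 1.96). With r = 0.20 and n = 140 it is 66%.

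*Every least-compliant patient removed (worst case).* For fraction f: c = z(f), λ = φ(c)/(1−f), v = 1 + cλ − λ². At f = 0.10, c = −1.282, λ = 0.195 and v = 0.712, so r_obs = 0.20 × 0.712 / √(0.954 × 0.928) = 0.151. With n = 140 × 0.90 = 126, power is 39%.

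*Half of those below the cut-off removed, same total f.* c = z(2f); mean m₁ = 0.5φ(c)/(1−f); second moment m₂ = [1 − 0.5(2f − cφ(c))]/(1−f); v = m₂ − m₁². At f = 0.10, c = −0.842, v = 0.845 and r_obs = 0.175.

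| f | Worst case: r; power at n=140(1−f) | Power at n=140 | Half removed: r; power at n=140(1−f) | Power at n=140 |
|---|---|---|---|---|
| 5% | 0.169; 49% | 51% | 0.179; 54% | 56% |
| 10% | 0.151; 39% | 43% | 0.175; 50% | 54% |
| 15% | 0.138; 32% | 37% | 0.176; 48% | 55% |

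Both sample sizes are shown because 140 is already a target after losses. A random loss of 10% would leave 61% power, so most of the worst-case fall comes from selection. These are nominal tests; A2.3 and I2 apply a Benjamini-Hochberg correction, which lowers all the power figures.

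**Which analyses are exposed.** A2.3 and I2 correlate baseline characteristics with the APS trend, and the primary endpoint is a change from baseline; a compliance pathway can operate in all of these. The A3 response is a within-patient contrast of days with and without a treatment, among patients treated on some days only. A path through intake lies largely outside that contrast, so for A3 the loss of partial adherers mainly shrinks the eligible set.

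**Gain from using all enrolled.** The detectable correlation at 80% power is tanh[(1.960 + 0.842)/√(n−3)]: 0.235 at n = 140 and 0.208 at n = 180, if all 180 have usable outcomes.

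**The case against.** The strongest reply is that the rule is narrower than it looks. Protocol 8.5.1 is headed as compliance to protocol and speaks of following instructions. The examples in 5.8.1 are missed visits and failed contact, the latter classed as lost to follow-up. The current 8.5.3 attaches nothing to low analgesic intake, and the amendment summary shows that a sentence linking the two was removed. The rule is permissive, each discontinuation is discussed between investigator and sponsor, and Protocol 8.5.2 does not treat timing deviations as violations. Discontinued patients are still reported in the Clinical Study Report, and diary scores up to discontinuation exist. On this view the defect is the SAP's completer set, not the protocol rule.

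Much of this stands. A reader might infer that patients who take little of their prescribed analgesic are removed. The documents do not say so: 8.5.1 is broad enough to allow it, but 8.5.3 does not provide for it. A reader might also infer that trait effects are biased towards zero. That needs traits to act mainly through compliance without an opposing direct effect, and no document states this.

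What does not fall away is that the broad sentence in 8.5.1 remains, no threshold limits it, and it serves no purpose in a study that leaves care untouched. The completer set makes the consequence worse, but changing that set would not restore Visit 2 assessments never made.

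**Conclusion.** The point holds as a question of avoidable selection. Discontinuation for non-compliance, dropout status, no replacement and a completers-only analysis are all in the documents, and the SAP set conflicts with the protocol's all-enrolled set. Direction and size are unknown, because the documents give neither the number likely to be discontinued nor any link between traits and compliance.

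The illustrative loss, from r = 0.20 and 66% power to about 0.18 and 48 to 56%, assumes full mediation, a = 0.4, b = 0.5, 5 to 15% removed and discretionary removal. The lower figures, down to 0.138 and 32%, are a worst case. A firm claim of bias towards zero, or that low analgesic intake leads to removal, goes beyond the text. The change should be made, since it costs little and removes a source of bias that could not be corrected afterwards.

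**What to change.** 1. Delete the discontinuation sentence in Protocol 8.5.1 and limit the non-compliance item in 5.8.1 to patients who cannot be contacted. Reconcile 5.8.1, 8.5.1 and 8.5.3 on what non-compliance means. The health-status grounds in 5.8.1 are not affected.
2. State that patients who miss diary entries, visits or prescribed doses stay under observation, with Visit 2 assessments collected, unless they withdraw consent.
3. Reconcile SAP section 4 with Protocol 10.1.1: include enrolled patients with available diary data, which Protocol 7.2.2.1 collects up to early discontinuation, and keep completers as a sensitivity analysis. Compare baseline traits of dropouts and completers.
4. Carry the 50% evaluation from 8.5.3 into the data file as a descriptive variable. Do not delete flagged intervals: the intermediate visit is optional, so a patient may have one interval only, and A3 needs the days without treatment.

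The cost is protocol and SAP wording and one sensitivity analysis. Some retained patients will have sparser diaries. In the two-visit scenario, MHLCS, HADS, LOT-R and PCS are collected only at Visit 1B, so patients lost before then lack those traits and need imputation or a stated exclusion.

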8.5.2. COMPLIANCE TO TIMING OF PROCEDURES

The Investigator should make a reasonable attempt to complete the scheduled study procedures on the appropriate scheduled visit and in the appropriate sequence.

The specifications in this protocol for the sequence of procedures are given as targets, to be achieved if possible.

It is recognized that deviations may occur for logistic or other reasons and will not be considered as protocol violations. The scheduled timepoints may be subject to alterations; however, the actual time must always be correctly recorded in the CRF, diary or other documents.

8.5.3. COMPLIANCE TO ANALGESIC PATIENT 'S THERAPY

Patient's compliance to prescribed analgesic medication will be assessed at each visit by direct questioning and checking diary. The investigator will evaluate if patient fails to take more than 50% of the prescribed analgesic medication for the visit interval.

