Diary:	The following information will be collected daily in the diary: APS and Worst Pain Score (WPS) for the past 24-hours, intake of additional to prescribed analgesic treatment (rescue analgesic treatment).
Study Evaluation Criteria and methods:	
Patient general health status	Symptoms related to analgesic treatment will be listed, and if the frequency of symptoms allows, they will be summarized using descriptive statistics.
Pharmacokinetic	Not applicable
Pharmacodynamic	Analysis of subjective changes from baseline of pain severity as measured by the weekly means of the daily APS and WPS, by Brief Pain Inventory (BPI), Investigator Global Assessment of Change (IGAC) and Patient Global Assessment of Change (PGAC), QLQ-C30 will be performed. In addition, analysis of quantitative changes measured by MPA, SA, MDA, MPT and TPS will be performed and compared between enrolment Visit and Visit 2. These tests will be listed and summarized using standard descriptive statistics. Additional analysis will be performed if warranted upon data review
Statistical Analysis:	Both effects on subjective and quantitative measures will be analyzed using Statistical Learning approaches potentially including covariates to be described in the Statistical Analysis Plan (SAP).
Safety:	Not applicable
Exploratory measures:	For patients who give their consent, archived tumor tissue block, if any and/or aliquot of standard safety laboratory blood sample will be used for genotyping exploratory research.
Interim Analysis	A preliminary analysis will be scheduled after approximately 60 patients complete the study

Table of Contents

1. Synopsis.....	3
2. Study Objectives and Endpoints.....	10
2.1. Primary Objective	10
2.2. Primary Endpoint	10
2.3. Secondary Endpoints	10
3. Study Background Information	11
3.1. Investigational Medicinal Product(s) Name(s).....	11
3.2. Introduction - Literature and/or Data Background	11
3.3. Rationale for the Study	15
4. Study Design	16
4.1. Description of Study Design	16
4.1.1. Screening and Enrolment Visit.....	17
4.1.2. Observational Period – Intermediate Phone Call	20
4.1.3. Visit 2: End of Observational Period and Follow-up Visit.....	21
4.2. Rationale for the Study Design	21
4.2.1. Population Selection and Sample Size.....	21
4.2.2. Justification for Study Design.....	22
4.2.3. Interim Analysis	22
5. Population Recruitment, Enrolment and Withdrawal	23
5.1. Definitions	23
5.2. Population Recruitment	23
5.3. Inclusion Disease Criteria.....	23

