14. Publication Policy	45
15. Literature and Data References	46
16. Attachments	49
16.1. Attachment 1 – Study Schedule – Enrolment at visit 1	49
16.2. Attachment 2 – Study Schedule – Enrolment and Screening at visit 1A	51
16.3. Attachment 3 – List of Definitions and Abbreviations.....	53
16.4. Attachment 4 – Protocol Amendment Summary	55
2.3 Secondary Endpoints	56
3.2 Introduction - Literature and/or Data Background	57
4.1. Description of Study Design	57
4.1.1. Screening and Enrolment Visit	60
5.1. Definitions	66
5.2. Population Recruitment.....	66
5.3. Inclusion Disease Criteria	66
5.5. Exclusion Disease Criteria	66
5.6. Exclusion Criteria	67
5.11. Discontinuation of Study	67
6.3. Concomittant Therapy.....	67
7.1. Study Patient Management and Requirements	67
7.2. Study Restrictions	68
8.2.3. Pain Disease Evaluation.....	70
8.2.4. Pain Evaluations	70
8.2.5. Quality of Life Questionnaires (QLQ) Quality-of-Life Questionnaire in 30 questions (QLQ-C30)	70
8.3. Information on General Health Status	71
8.3.1 Symptoms Monitoring	71
8.4. Study Procedure Priority Order.....	72
16.1 Attachment 1 – Study Schedule	75
16.1 Attachement 1 - Study Schedule – Enrolment at Visit 1	77
Section 16.2. Attachment 2 – Study Schedule – Enrolment at Visit 1A was added.....	79

Rationale for Protocol Amendment

Protocol T2001-01 version 1.0, An Observational Study to Collect Data Characterizing Analgesia in Patients Suffering from Bone Metastasis induced Pain. The new protocol version is version 2.0 and will be used to conduct the study in place of the preceding version.

The overall changes and rationale for the changes made to this protocol are as follows:

- Study design, study schedule and related sections were modified to give patients more flexibility to perform study procedures. Visit 1 and previous Visit 2 procedures can be performed either on the same visit or 2 different ones, allowing enrolment to take place at the first patient visit. Previous Visit 3 is now made optional. The numbering of the visits was therefore reviewed throughout the entire protocol.
- The number of questionnaires to be completed by patients during the study was decreased: QLQ-BM22 is no longer used and QLQ-C30 will only be performed twice.
- The information to be collected in the diary was also significantly decreased. Patients will only be asked to daily report APS, WPS and intake of additional rescue medication.

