7.2.2.1. Diary

Once a day from enrolment till Visit 2, approximately at the same time of the day in the evening, patients will complete their diary.

The following data will be recorded:

- pain intensity assessment by recording APS and WPS for the last 24 hours (from enrolment till Visit 2 or early discontinuation). See Sections 8.2.4.4 and 8.2.4.5 for further description of APS and WPS,
- any potential event that may help to understand unexpected study outcomes,
- intake of rescue analgesic treatment if any (from enrolment to Visit 2 or early discontinuation).

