8.5.5. COMPLIANCE TO DIARY COMPLETION

Compliance to diary completion (APS, WPS, rescue analgesic treatment recording) will be checked by Investigator at each visit at Investigator site.

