4.2 Study Participant Characteristics

The following variables will be recorded and may be used as quantitative or classification variables:

- Patient characteristics, measured at V1:
 - Study center
 - Patient's sociodemographic characteristics: age, sex and other demographic characteristics
 - Recent analgesic treatment history
 - Personality questionnaires, at facet- and domain-level: Multidimensional Health Locus of Control Scale (MHLCS, with domains I, C and P), Hospital Anxiety and Depression Scale (HADS), Revised Life Orientation Test (LOT-R) and Expectation.
 - Pain evaluation questionnaires: Douleur Neuropathique en 4 questions (DN4), Neuropathic Pain Symptom Inventory (NPSI), and Pain Catastrophizing Scale (PCS)
- Pain and quality of life assessment, measured at V1 and V2:
 - Brief Pain Inventory (BPI)
 - Quality of Life questionnaire in 30 questions (QLQ-C30), IGAC, PGAC
 - Clinical Pain Assessment (CPA): Static Allodynia (SA), Dynamic Mechanical Allodynia (DMA), Mechanical Pain Threshold (MPT), Thermal Pain Sensitivity (TPS)
- Follow-up from the daily diary and intermediate visit:
 - Daily Average and Worst Pain Score (APS and WPS),
 - Daily analgesic therapy (including rescue medication): number of distinct drugs intaken, number of distinct drug categories intaken
 - Intake of rescue analgesic treatment if any,

Note that the description of analgesic therapy hereabove requires the grouping of drugs into a small number of classes which will be described in the Statistical Analysis Report.

The collection of the values of all these variables and variables derived from them for a single patient is referred to as *the patient-vector* below in the text.

5 Description of the Analyses

The final statistical analysis covers four aspects (Ax) detailed in the following sections:

- A1: Descriptive statistics at baseline, covering secondary objectives number 1 and 2.
- A2: Evolution of daily pain and treatments, covering secondary objective number 3.
- A3: Prediction of treatment efficacy, covering the primary objective

In addition, the interim statistical analysis will cover the following two aspects, corresponding to the interim objectives:

- I1: Sample size computation for the prediction of treatment efficacy.
- I2: Relation between psychological traits and pain evolution

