The linear approximation of APS was chosen in order to describe the globally increasing or decreasing trend, while keeping easily interpretable results and avoiding overfitting. How to measure these values for one patient p:

- consider a model $APS_p(t) = a_{p0} + a_{p1} t$ where p is one patient and t is the time (in days since inclusion of patient p)
- Fit weights a_{pi} by linear regression on the patient's data (one dataset per patient, one record per timepoint)
- The variability around trend is measured by the per-patient RMSE of the linear model

Univariate statistics (mean, standard deviation (SD), median, first and third quartiles) on the distribution of these variables will be reported in Table (tab-pain-evol-distr). A one-sample Wilcoxon signed rank test will be performed in order to determine whether the linear trend in APS is globally different from zero. In addition, visualisation of the patients based on these 3 features will be performed in Figure (5).

A2.2: Summary of individual analgesic treatment evolution 5.2.2

Based on the description of analysic therapy in the patient diary, the daily number of distinct drugs will be computed as well as the daily number of distinct drug categories. Treatment doses will be ignored for this analysis. The same feature extraction as in A2.1 will be performed on these daily numbers of drugs in order to obtain a per-patient average and linear trend of the number of drugs.

Univariate statistics (mean, standard deviation (SD), median, first and third quartiles) on the distribution of these variables will be reported in Table (tab-treat-evol-distr). A one-sample Wilcoxon signed rank test will be performed in order to determine whether the linear trend in number of analgesics is globally different from zero. In addition, visualisation of the patients based on these features will be performed in Figure (6).

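### SAP A2.2 counts all analgesics from a diary that records only rescue intake, and A3 has no stated source of daily exposure to prescribed drugs

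*Protocol*

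**What the plan says.** **Diary content.** The protocol synopsis describes the drug item as "intake of additional to prescribed analgesic treatment (rescue analgesic treatment"). Protocol 7.2.2.1 lists the pain scores, a free item for events that might explain unexpected results, and "intake of rescue analgesic treatment if any (from enrolment to Visit 2 or early discontinuation"). The rationale for version 2.0 presents this as a deliberate reduction: "Patients will only be asked to daily report APS, WPS and intake of additional rescue medication". Protocol 8.5.5 names the same items when it defines what is checked: "Compliance to diary completion (APS, WPS, rescue analgesic treatment recording").

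**What the SAP takes from it.** SAP 4.2, under a heading that covers the diary and the intermediate visit, lists "Daily analgesic therapy (including rescue medication): number of distinct drugs intaken", with rescue intake as a further separate item. SAP 5.2.2 (A2.2) relies on the therapy described "in the patient diary, the daily number of distinct drugs will be computed as well as the daily number of distinct drug categories". It then fits a per-patient mean and linear trend and tests the trend with a one-sample Wilcoxon signed rank test. SAP 5.3 (A3) builds one model per treatment. Its response is the difference in daily APS between on-days and off-days, in patients who took the drug on only part of their follow-up. A3 names no data source for exposure.

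**Compliance.** Protocol 8.5.3 has compliance to prescribed analgesics judged at every visit "by direct questioning and checking diary". Footnote c of both study schedules names the same two sources.

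**The concern.** The variable the SAP defines and the source it names do not match. A count that is meant to include prescribed and rescue drugs is drawn from a record that holds only rescue drugs. This would give a wrong result under the right label: a table and a test headed as the trend in number of analgesics would show the trend in rescue use.

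The loss falls on what the SAP says it wants to see. SAP 1.3 and 5.2 both stress that therapy changes often during follow-up. A prescribed drug started, stopped or switched after enrolment leaves no mark in the diary's drug item.

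A3 is more exposed because it serves the primary objective, and interim analysis I1 (SAP 5.4.1) reruns it at decreasing sample sizes to confirm the target of about 140 completers. If A3 used the only daily drug record that is specified, it could model rescue drugs alone. Rescue tends to be taken on worse days, so the on/off APS difference would partly reflect when patients hurt, and an effective drug could look harmful.

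**Working it through.** The plan gives no figure for this point, so there is none to reproduce. The check sets each use of drug data beside its source, followed by a small illustration.

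| Use | Needs | Source named | Does the diary hold it? |
|---|---|---|---|
| A2.2 daily counts (SAP 4.2, 5.2.2) | All analgesics, day by day | Diary in 5.2.2; diary and intermediate visit in 4.2 | Rescue only |
| A3 on/off days (SAP 5.3) | Each treatment, day by day | None | Rescue only |
| Compliance (protocol 8.5.3, footnote c) | Prescribed intake per visit interval, against 50% | Direct questioning and diary | No |

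The intermediate visit does not close the gap in the first row. Protocol 4.1.2 makes it optional, and one visit cannot supply a daily series.

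Other places where on-study prescribed drugs might be recorded:
- Protocol 6.3 assigns to the CRF the analgesics of the month before enrolment and the primary disease medication. It does not mention on-study analgesics.
- Protocol 10.1.5 says that all prescribed analgesic treatment will be listed.
- Protocol 10.1.1.1 counts CRF entries among the data sources.
- The schedule in 16.2 has an analgesic treatment review row across visits, and the final call (4.1.3) asks about current treatment.

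Some prescription-level record is therefore implied, but no daily record of prescribed intake is specified and no start or stop dates are mentioned.

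**Illustration (assumed data).** 28 diary days, two prescribed drugs taken every day, and one different rescue drug taken on 10 days.
- Diary mean: 10/28 = 0.36 drugs per day.
- Full mean: 2 + 10/28 = 2.36 drugs per day.

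Now add a third prescribed drug on days 15 to 28. Its contribution to the least-squares slope is the sum of (t − 14.5) over those days, divided by the sum of (t − 14.5)² over days 1 to 28.
- Numerator: 0.5 + 1.5 + … + 13.5 = 98.
- Denominator: (28³ − 28)/12 = 1827.
- Contribution to the full slope: 98/1827 = 0.054 drugs per day. Contribution to the diary slope: 0.

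The sign can mislead too. Suppose a patient's only analgesic is taken daily as rescue on days 1 to 14 and is then prescribed and taken daily from day 15. The full count is 1 every day, with slope 0. The diary slope is −98/1827 = −0.054, an apparent fall in analgesic use where there was none.

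**For A3.** The drug added on day 15 has 14 on-days and 14 off-days, so the patient belongs in its model. From the diary alone the drug has no on-days, and the patient drops out. The two drugs taken every day are outside A3's scope whatever the diary records.

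**The case against.** The best defence is that A3 is not tied to the diary. It names no source, and protocol 10.1.1.1, 10.1.5, 16.2 and 4.1.3 all point to prescription information held elsewhere. On/off days might be built from that. This stands. A reader might infer that prescribed drugs are invisible to A3, but the documents show only that the SAP does not say how its exposure days are derived.

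A reader might also infer that compliance cannot be assessed. That goes too far: direct questioning is a named source and can support the 50% judgement. What remains is a misalignment of wording with the diary content.

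Nor can the diary be blamed for leaving out of A3 a patient on two regular drugs, or one whose new drug starts at Visit 1 and is taken daily. A3 excludes drugs taken throughout follow-up by design. Those cases show a loss in A2.2 only.

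Two further points are fair. A2.2 is a supporting summary and leaves the primary endpoint, change in weekly mean APS, untouched. And prescription dates do not remove confounding: protocol 4.1 has treatment reviewed according to patient need, so exposure built from dates still follows pain and becomes largely a before/after contrast.

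None of this reconciles A2.2 with its source. Its text names the diary and nothing else.

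**Conclusion.** The point holds for A2.2 as a contradiction between documents. Followed literally, the analysis and its Wilcoxon test measure rescue use and omit every prescribed drug, including those started, stopped or switched during follow-up. The amount of distortion depends on the mix of prescribed and rescue drugs, which the documents do not give. The figures above are illustrations on assumed data, not estimates for this trial.

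For A3 the point is a missing definition. No source of daily prescribed exposure is specified for the analysis that covers the primary objective and informs the interim sample-size decision, so it cannot be reproduced from the SAP. The damage is conditional: if the diary is used, only rescue drugs can be modelled and their on-days would tend to be high-pain days. That tendency is a clinical assumption, not a figure from the documents. The A3 gap concerns prescribed drugs whose use varied during follow-up.

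For compliance, the diary adds nothing on prescribed intake, and the check rests on direct questioning.

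**What to change.** 1. Confirm whether the CRF holds on-study start and stop dates for prescribed analgesics. Protocol 6.3 does not say so.
2. If it does, state in SAP 4.2, A2.2 and A3 that daily exposure to prescribed analgesics comes from the prescription records to be listed under protocol 10.1.5, and that only rescue intake comes from the diary. Give the rule that turns dates into exposure days, and report prescribed and rescue drugs separately.
3. If it does not, relabel A2.2 and A3 as rescue-only and limit the conclusions accordingly.
4. Align protocol 8.5.3 and footnote c of both schedules with the diary content, so that compliance to prescribed drugs rests on direct questioning.

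The cost is SAP and protocol wording plus a merge of prescription dates with diary days. It needs no new collection only if the dates already exist. Steps 1 to 3 should be settled before the interim transfer, because I1 reruns A3. The drawbacks are that exposure is as prescribed rather than as taken, and that confounding by indication remains and should be stated when A3 is reported.
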